## 11.2 Consent

The Informed Consent form must be approved by the REC and must be in compliance with GCP, local regulatory requirements and legal requirements. The investigator or designee must ensure that each trial participant, or his/her legally acceptable representative, is fully informed about the nature and objectives of the trial and possible risks associated with their participation.

The investigator or designee will obtain written informed consent from each participant or the participant's legally acceptable representative before any trial-specific activity is performed. The informed consent form used for this trial and any change made during the course of this trial, must be prospectively approved by the REC. The investigator will retain the original of each participant signed informed consent form.

Should a participant or participants legal representative require a verbal translation of the trial documentation by a locally approved interpreter/translator, it is the responsibility of the individual investigator to use locally approved translators. A locally translated PIS will also be provided if required.

## Consent must be taken prior to study randomisation.

Where potential patients fulfil the eligibility criteria, they will be approached by a member of the research team who will provide the patient information sheet and clarify any information from the patient which may preclude recruitment. Wherever possible informed consent will be obtained from the patient, however, due to the nature of the condition, this may not be possible.

## Patient legal representative available in the hospital

In patients lacking capacity, a legal representative will be sought. If the legal representative is available in the hospital, is contactable, or is due to visit the patient within a reasonable timescale, then they will be provided with information about the trial and asked if they will provide consent for the patient before enrolment. This will take place during their visit to the patient.

For the purposes of sites in England, Wales and Northern Ireland, a legal representative is defined as:

A person not connected with the conduct of the trial who is:

(a) Suitable to act as the legal representative by virtue of their relationship with the adult, and (b) Available and willing to do so.

For the purposes of sites in Scotland, a legal representative is defined as:

(a) Any guardian or welfare attorney who has power to consent to the adult's participation in research.

(b) If there is no such person, the adult's nearest relative as defined in section 87(1) of the Adults with Incapacity (Scotland) Act 2000.

#### Patient legal representative not available in the hospital

Due to the condition of these patients, there will be those who will have no registered legal representative or where the legal representative is not contactable or able to visit the hospital at short-enough notice to be able to enrol the patient in a timely manner. In such cases we advocate enrolment would be possible with written agreement from an independent clinician. Starting the study drug as soon as possible after admission to the NSU is perceived to gain maximum effect of a 7 day course of an AED. If no legal representative is available for discussion then an independent clinician will be approached. If a legal representative visits the hospital at a later date then the trial will be discussed with them and their consent sought at that time point to continue in the trial.

Patients who regain capacity whilst in hospital will be informed about the clinical trial and consent to continue will be sought. If at any stage either the legal representative or the patient chose to withhold consent then the patient will be withdrawn from the trial.

Patients who regain capacity following discharge will be contacted by phone and posted a patient information sheet and consent from as soon as possible.

#### Independent healthcare professional (IHP) definition

For the purposes of the MAST trial, the Independent Healthcare Professional (IHP) is defined as:

A person who is not connected with the conduct of the trial, specifically:

- a) The sponsor of the trial;
- b) A person who undertakes activities connected with the management of the trial;
- c) An investigator of the trial or;
- d) A health care professional who is a member of the investigators delegated team for the purposes of the trial.

Any new information which becomes available, which might affect the participant's willingness to continue participating in the trial will be communicated to the participant as soon as possible, verbally if the participant is in hospital, by post if they have been discharged.

The Medicines for Human Use (Clinical Trials) Regulations prohibit children under the age of 16 from giving consent to take part in CTIMP. Therefore consent will be sought on behalf of children from parents or a legal representative. Whenever practical and appropriate, the child's assent will be sought.

A flowchart depicting the consent process is illustrated in Figure 2.

[figure not shown]

Figure 2: Flowchart of the consent process

## 11.3 Screening evaluation

## 11.3.1 Screening Assessments

Trial specific assessments will only be conducted after participants have given written informed consent. Medical history which would preclude eligibility will be obtained from either the patient case notes or after discussion with the patient (or patient's representative – if available).

## 11.3.2 Participant Registration/Randomisation

Upon completion of consent and screening, patients are enrolled to either MAST-DURATION or MAST-PROPHYLAXIS based on their clinical presentation. A unique participant ID will be allocated to each patient. The initial section of the CRF will then be completed.

All patients enrolled into MAST-DURATION will be provided with a study wristband, to be applied before their first dose of medication and worn whilst they are an inpatient. This highlights that they are taking part in a research study and are receiving either phenytoin or levetiracetam. This is to help ensure the nursing staff at onward community hospitals or rehabilitation units are aware of the study at all times, and to ensure continuity of prescribed treatment. Wording on the wrist bands will read 'MAST TRIAL. PLEASE GIVE DRUG AS PRESCRIBED'.

All patients enrolled into MAST-DURATION will also be provided with a participant ID card. This is in case they need to show it to anyone who gives them medical attention and contains the name of the trial, whether they are receiving phenytoin or levetiracetam, the duration of the treatment and contact details for the local research site team and sponsor.

Patients enrolled in MAST-PROPHYLAXIS will not require a participant ID card or wristband as they are unlikely to leave hospital before the 7 days of treatment is complete.

Following randomisation, a letter will be sent to the patient's GP for both trials, informing the GP about the patient's participation, including which drug they are receiving, the duration of treatment and follow-up assessments. GPs will be advised that any further prescribing requirements will be forwarded in the discharge summary, as per routine clinical practice.

An anonymised record of the patients approached along with the numbers of, and reasons for, screen failures and refusal of consent will be kept at each site on a screening log and reported to the Trial Co-ordinating Centre on a monthly basis. This information will be used to identify any barriers to recruitment and allow improvement measures to be identified and implemented in a timely manner.

# 11.4 Screening & Baseline Assessments

All patients will have a medical history taken and a clinical examination as part of the routine standard care. The following are to be recorded in part 1 of the case report form (CRF):

- Inclusion/exclusion criteria review
- Informed consent process followed and consent or authorisation for enrolment
- Obtained
- Urine pregnancy test (if applicable) for females of child bearing potential
- Routine review of clinical laboratory results
- ECG (if indicated by local policy)
- Standard of Care:
  - Patient medical history (including co-morbidities and relevant medications)
  - Patient demography
  - Injury related events date of TBI, date of PTS, date of possible intubation, date of AED
  - Neurological status
  - o Imaging review

## 11.5 Trial assessments

## 11.5.1 Timing of assessments

Patients will be monitored as per routine clinical practice in the Neurosurgical Unit until discharge and thereafter at 6 months, 12 months, 18 months and 24 months (+/- 8 weeks at each time point) in both studies to score clinical outcome. Patients in the MAST-PROPHYLAXIS study will also be followed up at 14 days. Patients from the MAST-PROPHYLAXIS study may also be followed up at 60 months, subject to additional funding (+/- 8 weeks).

11.5.2 Assessments at time point

- Adverse events of special interest review during treatment.
- Assessment for seizures during hospital admission, at discharge at day 14 (by telephone if patient is already discharged) (PROPHYLAXIS only)
- EQ-5D-5L questionnaire at discharge

Follow up postal questionnaire/email/telephone call at 6 months (+/- 8 weeks), 12 months (+/- 8 weeks), 18 months (+/- 8 weeks), 24 months (+/- 8 weeks) post randomisation
 To document:

Occurrence of seizures

- GOSE questionnaire
- NSI questionnaire
- EQ-5D-5L questionnaire
- Liverpool Adverse Events Profile questionnaire

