	
 
Inclusion Criteria:
 
Patients aged ≥10 years with TBI managed in an NSU who have started on phenytoin or levetiracetam due to an acute symptomatic seizure during acute hospitalisation
 
Patient or Legal Representative is willing and able to provide informed consent or in the absence of a legal representative, an Independent Healthcare Professional provides authorisation for patient enrolment
 

	
 
Exclusion Criteria:
 
Un-survivable injury
 
Previous history of epilepsy
 
Patients who are on an AED pre-TBI
 
Patient who has been clinically prescribed an AED to treat PTS (other than phenytoin or levetiracetam) since current admission
 
Any hypersensitivity to study drug selected or any of its excipients
 

Investigational medicinal product	Phenytoin as prescribed clinically
and dosage	Levetiracetam as prescribed clinically In MAST-DURATION the choice of AED (phenytoin or levetiracetam) will be at the discretion of local clinical teams.
Route(s) of administration	Oral, nasogastric tube, IV
Maximum duration of treatment of a participant	MAST-PROPHYLAXIS: 7 days MAST-DURATION: Up to 24 months dependent on clinical need
Procedures: Screening & enrolment	Review of clinical situation (TBI patients) will be undertaken by a member of the clinical team. Informed consent will be obtained from the patient, patient's representative (if the patient lacks capacity) or by agreement with an independent clinician.

Procedures: Baseline	
 
Inclusion/exclusion criteria review
 
Informed consent process followed and consent or authorisation for enrolment obtained.
 
Standard of Care
 
Patient medical history (including comorbidities and relevant medications) and patient demography
 
Neurological status
 
Imaging modality and date of examination
 
Presence of PTS during the treatment period / after the prophylaxis
 
				
Procedures: Treatment period	
 
Standard clinical monitoring to discharge
 
Follow up at 14 days (PROPHYLAXIS)
 
Follow up at 6 months (+/- 8 weeks)
 
Follow up at 12 months (+/- 8 weeks)
 
Follow up at 18 months (+/- 8 weeks)
 
Follow up at 24 months (+/- 8 weeks)
 
				
Procedures: End of trial	The date of the last patient's final assessment/loss to follow-up.				

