#### 8.6 Trial Outcome Measures

#### 8.6.1 Primary outcome measure

**MAST-PROPHYLAXIS:** Occurrence of an acute symptomatic seizure within 2 weeks post-TBI. **MAST-DURATION:** Occurrence of late PTS within 24 months post-TBI

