#### 14.1.3 PTS recurrence

PTS recurrence will be measured from the date of randomisation to the 24 month follow up and will be reported for all causes.

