## 16 Statistics

### 16.1 Statistical methods

The main statistical analysis will be performed on an intention-to-treat basis, which will include all randomly assigned participants.

The primary endpoint (occurrence of PTS) is binary (yes / no). The primary analysis will estimate the absolute difference between the active treatment groups and control in terms of the incidence of PTS using logistic regression with an additive link, adjusting for baseline covariates (subdural haematoma (yes / no), number of lobes with a contusion (none / one / two / more than two), craniotomy or craniectomy (yes / no), depressed skull fracture (yes / no), initial severity of injury GCS 3-8 / 9-15, intradural lesion (yes / no) and will furnish the estimates with 95% confidence intervals. MAST DURATION will use a standard 2-sided p-value compared to a 5% significance level; MAST-PROPHYLAXIS will adjust for multiple testing using Dunnett's test at an overall 5% significance level stipulating that the smaller of the 2-sided p-values must be less than 2.7% to achieve statistical significance. A direct comparison between active arms (phenytoin vs levetiracetam) in MAST-PROPHYLAXIS will be a secondary analysis. The baseline covariates will be those used to stratify the randomisation: depressed skull fracture (yes / no), intradural lesion (yes / no) and initial severity of injury (GCS 3-8, GCS 9-15). Site will be handled as a random effect as there are anticipated to be 29 sites.

Sensitivity analyses will be performed to assess the influence of missing data and deviations from the intention-to-treat principle.

The GOSE will be analysed with an ordinal method adjusting for baseline covariates. Further secondary endpoints will be summarized using appropriate techniques according to whether the variable is binary, categorical, continuous or time-to-event. Categorical and binary variables will be summarized using bar charts, frequency tables and comparisons made using logistic regression.

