#### MAST DURATION

A course of phenytoin or levetiracetam (up to 3 months) for patients with PTS in the acute phase. Hence, we are starting from the premise that the shorter AED duration is 'standard' practice. The longer AED duration course will potentially decrease the PTS rate. Therefore, the proposed study will be a superiority trial. In view of the potential for increase in side effects with a longer course, we will aim for a relatively large treatment effect of 13% (NNT 7.7), as this is felt necessary in order to lead to a change in clinical practice in the 'real -world'.

Recruiting 428 patients overall will provide 188 observations per arm. Assuming seizure rates of 12% and 25% in the intervention and control arm will provide 90% power. The expected average annual recruitment is 5-10 patients / site. We will aim to roll out the trial in 29 adult trauma-receiving hospitals in the UK. According to the timeline presented below, the recruitment will be completed in 3 years.

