# 16.7 Definition of the end of the trial

The end of the main trial will be the date of the last patient's final assessment/loss to follow-up.

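### MAST-DURATION: the last scheduled seizure enquiry may fall up to 8 weeks before 24 months post randomisation, so the end of the primary endpoint window is not always actively ascertained

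*Protocol*

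**What the plan says.** Protocol section 8.6.1 defines the MAST-DURATION primary outcome as "Occurrence of late PTS within 24 months post-TBI". Section 16.1 adds: "The primary endpoint (occurrence of PTS) is binary (yes / no"). The endpoint clock therefore starts at the injury, and the outcome is whether an event occurred at any time in a fixed period.

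The contact clock starts at randomisation. Section 11.5 places the later follow-up contacts at "18 months (+/- 8 weeks), 24 months (+/- 8 weeks) post randomisation", and the synopsis has "Follow up at 24 months (+/- 8 weeks"). Seizure occurrence is one of the items collected at these contacts, together with the GOSE, NSI, EQ-5D-5L and Liverpool questionnaires. The section 11.6 schedule heads the 24-month column as the end of study and shows no later contact for this trial.

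Section 14.1.3 says "PTS recurrence will be measured from the date of randomisation to the 24 month follow up", so it ties the close of measurement to the contact and not to a fixed 24 months.

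Two other provisions matter. The seizure definition text in section 8.5 asks participants to contact their treating team after a seizure and to tell the central coordination team, and the GP is sent a confirmation form. Section 16.5 assumes that missing data are missing at random.

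**The concern.** A symmetric visit window suits a score taken at one time, such as the GOSE or EQ-5D-5L, where a few weeks either way make little difference. It suits a cumulative event less well. A seizure question asked before 24 months cannot cover the time still to run.

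Under section 11.5, a questionnaire completed 8 weeks early is a valid final assessment. Section 11.7 treats a participant as lost to a follow-up only when there is no response by 8 weeks after the time point, so an early reply is a completed contact. With a yes/no endpoint and nothing further scheduled, an early reply of no seizure would probably be entered as no event. A first late seizure in the remaining weeks would then reach the data only if the participant reported it unprompted.

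At stake is mild under-ascertainment of the primary endpoint in both arms, which would pull both rates and their absolute difference slightly downwards. A SAP can restrict or recode what was collected, but it cannot recover an answer to a question that was not asked.

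**Working it through.** **Inputs from the protocol.** Seizure rates and power: "Assuming seizure rates of 12% and 25% in the intervention and control arm will provide 90% power" (section 16.3). Test: "MAST DURATION will use a standard 2-sided p-value compared to a 5% significance level" (section 16.1). Section 16.3 also gives 428 recruited, 188 observed per arm and 12% drop-out; allocation is 1:1 (section 9.3). Late PTS starts after day 7 (section 6.1).

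**Step 1: reproduce the plan's figures.**
- Observed per arm: 428 × 0.88 / 2 = 188.3, so 188. In reverse, 376 / 0.88 = 427.3, rounded up to 428.
- Pooled rate: (0.25 + 0.12)/2 = 0.185. SE under the null: √(2 × 0.185 × 0.815 / 188) = 0.0400.
- SE under the alternative: √((0.25 × 0.75 + 0.12 × 0.88)/188) = 0.0395.
- z = (0.13 − 1.96 × 0.0400)/0.0395 = 1.30, which gives power of 90.4%. The stated 90% and N = 428 both reproduce.

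**Step 2: size of the gap.** Eight weeks is 56 of 730.5 days, or 7.7% of 24 months. It equals 1.84 months, so the earliest in-window contact is at 24 − 1.84 = 22.16 months after randomisation. On the post-injury clock the gap is 56 days minus the days from injury to randomisation. The protocol gives no figure for that interval; the synopsis allows randomisation at any time in the acute neurosurgical unit stay.

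**Step 3: rates if observation stops early.** The at-risk period is day 7 to day 730.5, which is 723.5 days. Stopping 56 days early leaves 667.5 days, a fraction f = 667.5/723.5 = 0.9226. The protocol gives no seizure timing, so three shapes are assumed:
- Constant hazard: q = 1 − (1 − p)^f. For p = 0.25, q = 1 − 0.75^0.9226 = 23.3%. For p = 0.12, q = 1 − 0.88^0.9226 = 11.1%.
- Front-loaded (Weibull, shape 0.5): q = 1 − (1 − p)^√f, with √f = 0.9605.
- Linear accrual: q = p × f.

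**Step 4: power again with 188 per arm**, assuming nothing is captured outside the contacts.

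| Scenario | Control | Intervention | Difference (points) | Power |
|---|---|---|---|---|
| Window fully covered | 25.0% | 12.0% | 13.0 | 90.4% |
| All 8 weeks early, constant hazard | 23.3% | 11.1% | 12.2 | 88.2% |
| All 8 weeks early, front-loaded | 24.1% | 11.6% | 12.6 | 89.3% |
| All 8 weeks early, linear | 23.1% | 11.1% | 12.0 | 87.4% |
| As row 2, randomised day 14 (assumed) | 23.7% | 11.3% | 12.4 | 88.8% |
| As row 2, randomised day 28 (assumed) | 24.2% | 11.6% | 12.6 | 89.4% |
| Average 2 weeks missed, constant hazard | 24.6% | 11.8% | 12.8 | 89.9% |

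The last row matches contacts spread evenly over ±8 weeks: half are early, by 4 weeks on average, so the mean loss is 2 weeks.

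**Step 5: events.** In row 2, control loses 188 × (0.250 − 0.233) = about 3 of 47 expected events. Intervention loses 188 × (0.120 − 0.111) = between 1 and 2 of about 23.

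**The case against.** The strongest reply is that the protocol does not say what a hasty reading would have it say. Five points need separating.

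- **Coding.** A reader might infer that unobserved weeks count as seizure-free by rule. No section says so. Section 16.5 speaks only of missing at random, and the coding of an early reply may be in the SAP, which was not available. That no event would be recorded is a likely consequence of a binary endpoint, not a stated rule.
- **Capture.** A reader might infer that the last weeks go wholly unobserved. Section 8.5 provides a continuing reporting route through the participant, the treating team and the GP form, and nothing closes it at an early questionnaire. Section 16.7 ("The end of the main trial will be the date of the last patient's final assessment/loss to follow-up") defines the end of the whole trial, not of each participant's reporting. The route is passive, however, and the GP form confirms a reported seizure without searching for others. The gap is therefore one of active ascertainment.
- **Late side.** A reader might infer that seizures in months 24 to 26 would be counted. Section 8.6.1 excludes them by definition. Section 14.1.3 is looser and should be aligned, but it does not replace the primary outcome definition.
- **Arm-dependent timing.** The trial is open-label, so a reader might suspect contact timing that differs by arm. Nothing in the protocol suggests it. Section 11.7 describes posting and then telephone chasing, which delays replies and does not advance them.
- **Size.** The table assumes the passive route captures nothing, and its 8-week rows put every contact at the earliest permitted date. Actual loss should be smaller.

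These replies limit the point without removing it. A final seizure enquiry before the endpoint window closes is permitted, and no later enquiry is scheduled.

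**Conclusion.** The point stands as a minor, inexpensive improvement to ascertainment of the primary endpoint. Three passages do not fit together: the endpoint runs to 24 months post-injury (section 8.6.1), the last scheduled enquiry may come up to 8 weeks before 24 months post randomisation (section 11.5 and the synopsis), and measurement is said to close at that contact (section 14.1.3).

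The effect is small. With every contact at the earliest date and no other capture, the difference falls from 13.0 to between 12.0 and 12.6 points, and power from 90.4% to between 87.4% and 89.3%, over the three assumed event-timing shapes. With an average of 2 missed weeks, power is about 89.9%. Any delay from injury to randomisation shrinks the gap further. A reader might infer that the trial is underpowered or its sample size miscalculated; the figures do not support that, since both stated values reproduce. The case for acting is that the loss is avoidable and cannot be recovered at analysis.

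**What to change.** In section 11.5 and the synopsis, set the window for the final seizure question to 24 months -0/+8 weeks. Because randomisation follows the injury, a question asked no earlier than 24 months post randomisation is also never asked before 24 months post-injury. If a form is nevertheless completed early, repeat the seizure question at or after 24 months.

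Record the date of each seizure and count towards the primary outcome only late PTS dated within 24 months post-injury, so that the later contact does not lengthen the endpoint. Reword section 14.1.3 so that its measurement period matches section 8.6.1.

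Keep ±8 weeks for the GOSE, NSI, EQ-5D-5L and Liverpool scales, and for the 6-, 12- and 18-month contacts. Censoring early responders at the form date is not a suitable alternative, because it does not fit the binary regression in section 16.1.

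The cost is a wording change and a mailing-date rule. The downside is that some final contacts fall up to 8 weeks later.
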